6.4. Study Intervention Compliance

Participants will receive study intervention directly from the investigator or designee at the study site, under medical supervision. The date and time of each dose administered in the clinic will be

recorded in the source documents and recorded in the eCRF. Deviations from the prescribed dosage regimen should be recorded in the eCRF.

6.5. Concomitant Therapy

Participants will be instructed to consult the investigator or other appropriate study site personnel before taking any new medications or supplements during the study. The sponsor's medical monitor should be contacted if there are any questions.

Recording of concomitant therapy

Any medication or vaccine (including over-the-counter or prescription medicines, vitamins, and/or herbal supplements) that the participant is receiving at the time of enrollment or receives during the study must be recorded along with

- reason for use,
- route of administration, and
- dates of administration, including start and end dates.

For concomitant therapies of special interest, dosage information will also be collected as well as reason for use and route and dates of administration.

Allowed concomitant therapy

Participants will maintain their usual medication regimen for SLE and for any other diseases throughout the study unless specifically excluded in the protocol (Section 5.2). Doses must be stable prior to randomization, as stated in the exclusion criteria. Permitted concomitant background standard-of-care medications for SLE can include any combination of these:

- NSAIDs,
- a single antimalarial (such as hydroxychloroquine, chloroquine, or quinacrine),
- a single oral immunosuppressant from the following list: methotrexate, azathioprine, mycophenolate mofetil, or mizoribine,
- a single corticosteroid.

Dose adjustment for NSAIDs, antimalarials, and immunosuppressants

Doses of NSAIDs intended for treatment of signs and symptoms of SLE, antimalarials, and immunosuppressants should not be adjusted during the study's double-blind treatment period. Participants who require initiation or increase in dosage of NSAIDs for treatment of signs and symptoms of SLE, or of antimalarials, or of immunosuppressants after randomization may remain in the study and continue receiving study drug.

Dose adjustment for corticosteroids

See Section 6.5.1.

6.5.1. Corticosteroid Management Program

Key elements of the corticosteroid management program of this study include the following:

- Participants are restricted to prednisone ≤ 20 mg per day (or equivalent) at randomization (Visit 2), having been on stable doses for at least 2 weeks prior to randomization.
- Following randomization, the dose of prednisone (or equivalent) should not be increased above the participant's background level.
- Participants on >10 mg per day are required to taper their dose to ≤ 10 mg per day by Week 12 to be considered **responders**.
- The corticosteroid doses should not be changed after Week 18.
- Participants with intolerable or exacerbating disease are allowed access to standard-of-care therapy, including increasing the dose of prednisone (or equivalent). Such participants are allowed to remain in the study and continue receiving study drug, but they will be considered **nonresponders** for the efficacy analyses from the time of the medication change onward.

Guidance on corticosteroid tapering

The following guidance on corticosteroid tapering is provided for participants taking >10 mg prednisone (or equivalent) at baseline.

- Steroid tapering should begin no sooner than 4 weeks after randomization.
- Tapering should include a stepwise reduction in 2.5 mg/d to 5 mg/d increments, with each step reduction occurring at 2-week intervals. Thus, the stepwise reduction will occur in intervals that are consistent with the visit schedule.
- Participants who do not tolerate a reduction can increase the dose up to, but not exceeding, the dose at randomization.

Under this schedule, a participant on the highest allowed dose of 20 mg per day at randomization would taper his or her steroid dose in 2.5 mg per day increments at 2-week intervals to achieve the target of ≤ 10 mg per day in time for the assessments at Week 12.

Participants who are taking ≤ 10 mg prednisone (or equivalent) at baseline may have their dose tapered at the discretion of the investigator. However, the corticosteroid doses should not be changed after Week 18.

These recommendations recognize that there is variability in how corticosteroids are administered. The intent is to allow investigators flexibility in how corticosteroids are tapered for individual participants, provided that the participants reach the goal of ≤ 10 mg per day in time for the assessments at Week 12.

Concomitant therapy after permanent discontinuation of study drug

Standard-of-care therapy can be resumed after the participant is permanently discontinued from study drug.

6.6. Dose Modification

Modification of the dose of the study intervention is not permitted in this study.

6.7. Intervention after the End of the Study

LY3471851 will not be available to participants following completion of the study.

7. Discontinuation of Study Intervention and Participant Discontinuation/Withdrawal

In rare instances, it may be necessary for a participant to permanently discontinue study drug.

These sections describe reasons for a participant's

- permanent or temporary discontinuation of study drug (Section 7.1), or
- discontinuation (withdrawal) from the study (Section 7.2).

Discontinuation of specific sites or the trial as a whole ("stopping rules") are handled as part of regulatory, ethical, and trial oversight considerations in Appendix 10.1, Section 10.1.9.

7.1. Discontinuation of Study Intervention

Study drug may be permanently discontinued or temporarily withheld during the study.

Participants who permanently discontinue study drug early will undergo early termination procedures, which include

- an early termination visit (ETV)
- AND,**
- post-treatment follow-up visits, as shown in the SOA.

7.1.1. Criteria for Permanent Discontinuation of Study Drug

Data collection and safety follow-up when study drug is permanently discontinued

If study drug is permanently discontinued, the participant will remain in the study to have an ETV and post-treatment follow-up visits, as shown in the SoA (Section 1.3).

See the SoA for data to be collected at the time of discontinuation and follow-up and for any further evaluations that need to be completed. Safety follow-up is as outlined in the SoA (Section 1.3), Section 8.2 ("Safety Assessments), **CCI** of the protocol.

The presence or absence of a clinically significant ISR will not unblind participants and is therefore not a protocol deviation.

Criteria for permanent discontinuation of study drug

Possible reasons for permanent discontinuation of study drug include, but are not limited to, the following:

Participant decision

- The participant requests to discontinue the study drug.

Pregnancy

- The participant becomes pregnant during the study (see Section 8.2.5.1).

Safety considerations

- The participant develops any of the following conditions during the study:
 - malignancy (except for successfully treated basal or squamous cell skin carcinoma)
 - HIV/acquired immune deficiency syndrome (AIDS) infection
 - active TB infection or untreated LTBI (Section 7.1.2; Section 8.2.6)
 - HCV RNA positive (Section 8.2.8)
 - HBV DNA positive and clinical assessment consistent with HBV reactivation

Note: The HBV DNA result is to be confirmed if initial positive test result is positive but below the level of quantification (Section 7.1.2; Section 8.2.7). The participant is to be referred to, evaluated, and managed by a specialist physician with expertise in evaluation and management of viral hepatitis prior to discontinuation of any immunomodulatory and/or immunosuppressive therapy, including study drug. Timing of discontinuation from study drug relative to the initiation of any antiviral treatment for hepatitis is to be based on the recommendation of the consulting specialist physician, in conjunction with the investigator, and aligned with medical guidelines and standard of care.

- The participant answered "yes" to Question 4 or Question 5 on the "Suicidal Ideation" portion of the C-SSRS, **or** answered "yes" to any of the suicide-related behaviors on the Suicidal Behavior portion of the C-SSRS.

Note: A psychiatrist or appropriately trained professional may assist in the decision to discontinue the participant.

- The investigator, after consultation with the sponsor's designated medical monitor, determines that a systemic hypersensitivity reaction has occurred and is related to study drug administration.
- The participant has any of the following results on 2 consecutive samples taken at least 48 hours, but no more than 1 week, apart.
 - Total WBC <1000 cells/ μ L
 - ANC <500 cells/ μ L
 - ALC <200 cells/ μ L
 - Hemoglobin <6.5 g/dL
- The participant develops CRS. In consultation with the Lilly medical monitor, if an adverse event is deemed possibly or probably due to CRS based on the details and severity of clinical signs and symptoms, time course of symptom onset relative to study drug administration, and if possible, a cytokine panel from a blood sample obtained at the time of the event, the participant will be discontinued from study treatment, and will continue safety follow-up.
- The participant develops hypereosinophilia.
 - Participants with absolute eosinophil counts >1500 cells/ μ L and signs and/or symptoms of target organ involvement that is not consistent with lupus and/or with the

participant's lupus and medical history will be discontinued from study drug in consultation with the medical monitor. Participants will undergo appropriate medical evaluation, which should take into account the participant's known lupus and past medical history according to the participant's history and medical records, including previous imaging, biopsies and laboratory findings. Evaluation of target organ involvement will involve additional diagnostic tests as appropriate, including laboratory tests, imaging (for example, echocardiogram, CXR, computed tomography [CT] scan) and biopsies. New onset cardiac, pulmonary, and skin findings in the setting of peripheral eosinophilia will be considered as target organ involvement, unless attributable to other causes.

- Asymptomatic participants with an absolute eosinophil count >5000 cells/ μ L should have a repeat measurement to confirm the count. If the count is confirmed, the participant will be permanently discontinued from study drug and undergo appropriate medical evaluation.
- The participant has an adverse event or a SAE or a clinically significant change in a laboratory value that, in the opinion of the investigator, merits the discontinuation of the study drug and appropriate measures being taken.

Hepatic event or liver test abnormality

- Participants who are discontinued from study drug because of a hepatic event or liver test abnormality should have additional hepatic safety data collected via the hepatic eCRF packet. Discontinuation of study drug because of abnormal liver tests should be considered by the investigator when a participant meets one of the following conditions after consultation with the sponsor's designated medical monitor (see Section 8.2.9).
 - ALT or AST >8 times ULN
 - ALT or AST >5 times ULN sustained for more than 2 weeks
 - ALT or AST >3 times ULN and TBL >2 times ULN or international normalized ratio (INR) >1.5
 - ALT or AST >3 times ULN with the appearance of fatigue, nausea, vomiting, right upper-quadrant pain or tenderness, fever, rash, and/or eosinophilia ($>5\%$)
 - alkaline phosphatase (ALP) >3 times ULN
 - ALP >2.5 times ULN and TBL >2 times ULN, or
 - ALP >2.5 times ULN with the appearance of fatigue, nausea, vomiting, right upper quadrant pain or tenderness, fever, rash, and/or eosinophilia ($>5\%$).

Other reasons

- Unblinding: If an investigator, blinded site personnel who are performing assessments, or participant is unblinded to a participant's treatment assignment, the participant must be discontinued from the study drug and continue to post-treatment follow-up. In cases where there are ethical reasons to have the participant continue on study drug, the investigator must obtain specific approval from the sponsor's designated medical monitor for the participant to continue.

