7.1.2. Criteria for Temporary Interruption (Withholding) of Study Drug

7.1.2.1. Infection-Related Criteria for Temporary Withholding of Study Drug

Temporary withholding of study drug is required for the development of any of the following infection-related criteria during the study:

- Serious or opportunistic infections, as defined in Exclusion Criteria (Section 5.2). Study drug is to be withheld until resolution of all acute clinical signs and symptoms, and completion of all appropriate anti-infective treatment (exception for LTBI, noted below).
- Participants diagnosed with LTBI during the study are to be permanently discontinued from study drug unless the participant is a candidate for LTBI treatment, and is treated for LTBI as follows:
 - Study drug is temporarily withheld for at least the first 4 weeks of LTBI treatment.
 - After receiving at least 4 weeks of appropriate LTBI therapy (as per World Health Organization and/or the United States Centers for Disease Control guidelines), if there is no evidence of hepatotoxicity (ALT/AST must remain ≤ 2 times ULN) or other treatment intolerance, study drug may be resumed.
 - The participant must complete appropriate LTBI therapy to remain eligible to receive study drug.
- HBV DNA results that are reported as positive, or as detecting HBV DNA, but HBV DNA is below the level of quantification. The sponsor's designated medical monitor should be contacted regarding study status of the participant. HBV DNA testing is to be repeated as soon as is feasible. If HBV DNA is confirmed as positive, the participant must be permanently discontinued from study drug (Section 7.1).

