8.2.7. Hepatitis B Testing and Monitoring

Initial testing for hepatitis B virus (HBV) infection includes hepatitis B surface antigen (HBsAg) and antibody to hepatitis B core antigen (anti-HBc).

- If HBsAg is positive, the participant is excluded.
- If HBsAg is negative and anti-HBc is negative, the participant is not excluded.

- If HBsAg is negative and anti-HBc is positive, further testing for HBV DNA is required.
 - If the screening HBV DNA is positive, the participant is excluded.
 - If the screening HBV DNA is negative, the participant is not excluded. Repeat testing for HBV DNA is required at least every 3 months during the study (Section 1.3), with temporary withholding or permanent discontinuation of study intervention if HBV DNA is positive, as described in Section 7.1.2 and Section 7.1.1, respectively.

Management of enrolled participants with detectable HBV DNA during the study

If HBV DNA is detected during the study, the study drug will be temporarily withheld or discontinued and participants should receive appropriate follow-up medical care as described in Section 7.1.1 and Section 7.1.2.

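### Protocol 7.1.1, 7.1.2.1 and 8.2.7 do not agree on when detected HBV DNA leads to permanent rather than temporary stopping of study drug

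*Protocol*

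**What the plan says.** Three sections of the protocol deal with HBV DNA that turns positive after randomization.

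- **Section 7.1.1 (permanent discontinuation).** The list opens with "Possible reasons for permanent discontinuation of study drug include, but are not limited to, the following". Its HBV item is "HBV DNA positive and clinical assessment consistent with HBV reactivation". A Note under that item says "The HBV DNA result is to be confirmed if initial positive test result is positive but below the level of quantification", with cross-references to 7.1.2 and 8.2.7. The Note also calls for referral to, and evaluation and management by, a viral hepatitis specialist "prior to discontinuation of any immunomodulatory and/or immunosuppressive therapy, including study drug". It adds: "Timing of discontinuation from study drug relative to the initiation of any antiviral treatment for hepatitis is to be based on the recommendation" of that specialist, together with the investigator.
- **Section 7.1.2.1 (temporary withholding).** The trigger is "HBV DNA results that are reported as positive, or as detecting HBV DNA, but HBV DNA is below the level of quantification". Drug is withheld, the medical monitor should be contacted about the participant's status in the study, and the test is repeated. Then: "If HBV DNA is confirmed as positive, the participant must be permanently discontinued from study drug", with a reference back to Section 7.1.
- **Section 8.2.7 (testing and monitoring).** Participants who are anti-HBc positive and HBV DNA negative at screening are retested at least every 3 months, "with temporary withholding or permanent discontinuation of study intervention if HBV DNA is positive", by reference to 7.1.2 and 7.1.1. A further sentence requires that drug be withheld or discontinued whenever HBV DNA is detected on study, and again refers to those two sections.

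Protocol 9.4.1 counts a participant who permanently discontinues study drug before the end of treatment, for whatever reason, as a nonresponder.

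**The concern.** The protocol knowingly enrols anti-HBc-positive participants and schedules repeat HBV DNA tests for them, so a new positive result is a foreseen event. A site that receives one needs to know whether to interrupt drug or end it, and whether a specialist must see the participant first. The sections give different answers on both points. One attaches a clinical assessment and specialist evaluation to permanent stopping, one makes permanent stopping compulsory without mentioning either, and the third refers the reader to the other two.

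Two sites could therefore handle the same confirmed laboratory result differently under a safety rule, and each could cite the protocol. There is a smaller statistical consequence. Permanent discontinuation fixes the participant as a nonresponder, while a temporary interruption is not in the nonresponder list of Protocol 9.4.1. The same clinical course could then be scored differently according to the section followed.

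**Working it through.** The plan states no figure on this point and no formula applies. The check sets the rules side by side for each kind of result.

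| Case | Section 7.1.1 | Section 7.1.2.1 | Section 8.2.7 |
|---|---|---|---|
| (a) First result below quantification, repeat positive, no clinical reactivation | HBV item not met: clinical part missing | Permanent stop is mandatory | Withhold or discontinue |
| (b) Quantifiable result, no clinical reactivation | HBV item not met: clinical part missing | Not triggered: covers below-quantification results only | Withhold or discontinue |
| (c) First result below quantification, repeat positive, with clinical reactivation | HBV item met; specialist evaluation comes before stopping | Permanent stop is mandatory; silent on specialist and timing | Withhold or discontinue |
| (d) Quantifiable result, with clinical reactivation | HBV item met; specialist evaluation comes before stopping | Not triggered | Withhold or discontinue |

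**Case (a)** is the direct inconsistency. The 7.1.1 Note addresses this same below-quantification situation and points to 7.1.2, but it does not drop the clinical condition. The condition also looks deliberate, because the HCV item just above it in the list has none.

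**Case (b)** is a gap. Neither 7.1.1 nor 7.1.2.1 states a mandatory permanent stop, and 8.2.7 leaves the choice open. Comparing (a) with (b), the lower-level laboratory result carries the more explicit stopping rule.

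**Case (c)** agrees on the action but not on the sequence. Only 7.1.1 puts the specialist before discontinuation.

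**Case (d)** shows no conflict.

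**Which scheduled tests can matter for the endpoint.** The Schedule of Activities places on-treatment HBV DNA tests at Week 12 (Visit 9) and Week 24 (Visit 15), with another at an early termination visit.

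- The last dose is at Week 22 and there is none at Visit 15. The Week 24 test therefore falls 24 − 22 = 2 weeks after the last dose, and its result cannot cause early discontinuation of study drug.
- If the Week 12 result arrives after that visit's dose, the scheduled doses still to come are at Weeks 14, 16, 18, 20 and 22, which is five. The temporary-or-permanent question is therefore live for the Week 12 result.
- Response status changes only for a participant who meets all of these: anti-HBc positive and HBV DNA negative at screening, newly positive at Week 12, in case (a) or (b), and otherwise a SLEDAI-4 responder at Week 24.

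The documents do not give the number of anti-HBc-positive participants or an expected rate of new positivity, so the size of this group cannot be calculated.

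**The case against.** The best case for the plan is that the sections can be read as one pathway. The 7.1.1 list is expressly non-exhaustive, so a site that stops drug permanently under 7.1.2.1 breaches nothing in 7.1.1. The same list lets the investigator stop for a clinically significant laboratory change. The 7.1.1 Note points to 7.1.2, and 7.1.2.1 points back to Section 7.1, where the Note stands. One can therefore read: withhold, contact the medical monitor, confirm, then discontinue with specialist involvement. The monitor contact also makes divergent handling less likely.

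Much of this stands. It rules out the reading that 7.1.1 makes clinical reactivation a necessary condition for stopping and so flatly forbids what 7.1.2.1 commands.

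A reader might also infer that one site could go on dosing while another stops on the same result. The documents do not support that: 8.2.7 requires drug to be withheld or discontinued on any detected HBV DNA, with no quantification limit. The specialist's role in timing is also narrower than it may seem. It concerns timing relative to antiviral treatment and is shared with the investigator.

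Three things remain. The single-pathway reading does not explain why 7.1.1 keeps a clinical condition for a case in which 7.1.2.1 makes stopping compulsory. It leaves the quantifiable result in case (b) without a rule for choosing temporary or permanent stopping. And the monitor contact in 7.1.2.1 is followed by a mandatory step with no stated discretion, and without the specialist evaluation that 7.1.1 puts first.

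**Conclusion.** The point holds as an internal inconsistency in current text about temporary versus permanent stopping. For a confirmed below-quantification result without clinical reactivation, 7.1.2.1 mandates permanent discontinuation, while the 7.1.1 HBV item, one entry in a non-exhaustive list, attaches a clinical assessment and its Note puts specialist evaluation first. For a quantifiable result without clinical reactivation, neither section states a mandatory permanent stop, and 8.2.7 does not settle it.

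This is chiefly a matter of safety conduct. A reader might infer that the primary endpoint depends on which section a site follows, or that every anti-HBc-positive participant's response status is at risk at both scheduled tests. The documents do not support that. Only the Week 12 test can bear on it among scheduled tests, and then only for a would-be responder. No material effect on the trial-level comparison is claimed. Because 8.2.7 sets a minimum testing frequency, an extra test between Weeks 12 and 22 could raise the same question, but the documents give no basis for a count.

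The conclusion rests on the wording of the three sections and the dosing and testing schedule. It takes no view on which clinical rule is right. The passages should be reconciled.

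**What to change.** Reconcile Protocol 7.1.1, 7.1.2.1 and 8.2.7 into one rule, stated once and cross-referenced from the other places. For quantifiable and for below-quantification results separately, it should state:

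- what leads to withholding and what leads to permanent discontinuation;
- whether a clinical assessment of reactivation is part of the test for permanent discontinuation;
- where confirmation, medical-monitor contact and specialist evaluation fall in the sequence.

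The clinical content is for the sponsor to decide. The cost is a protocol clarification and notice to sites. Design, sample size and planned analyses do not change. Once the rule is single, the nonresponder definition in Protocol 9.4.1 can be applied uniformly to these participants without further edits.

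### The mandatory stop for a confirmed eosinophil count above 5000 cells/µL is worded for asymptomatic participants only, so those with symptoms attributed to lupus or another cause are not clearly covered

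*Protocol*

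**What the plan says.** Protocol 7.1.1 introduces its list with "Possible reasons for permanent discontinuation of study drug include, but are not limited to, the following". One safety bullet reads "The participant develops hypereosinophilia" and carries two sub-rules.

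- **First sub-rule.** Above 1500 cells/µL, drug is stopped in consultation with the medical monitor if there are "signs and/or symptoms of target organ involvement that is not consistent with lupus" and/or with the participant's own lupus and medical history. New-onset cardiac, pulmonary and skin findings alongside peripheral eosinophilia "will be considered as target organ involvement, unless attributable to other causes".
- **Second sub-rule.** It begins "Asymptomatic participants with an absolute eosinophil count >5000" cells/µL and asks for a repeat measurement. Then: "If the count is confirmed, the participant will be permanently discontinued from study drug".

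Two other items in the same list bear on the point. The cytopenia limits, introduced by "The participant has any of the following results on 2 consecutive samples", have no symptom condition. A general bullet covers adverse events or clinically significant laboratory changes that, "in the opinion of the investigator, merits the discontinuation of the study drug".

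The readable text does not say what *asymptomatic* means in the second sub-rule.

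**The concern.** A threshold as high as 5000 cells/µL would be expected to work as a backstop that applies whatever the participant's symptoms. As worded, the backstop depends on a word that fits this population poorly. Inclusion criterion [7] requires active arthritis and/or rash in everyone at screening and randomization, so at entry nobody is free of lupus manifestations. The organs singled out in the first sub-rule (heart, lung, skin) also overlap with SLEDAI-2K items listed in Protocol 10.7.4: pericarditis, pleurisy and rash. Attributing such a finding to lupus is therefore a realistic call.

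The literal result runs the wrong way. A symptom-free participant with a confirmed count above 5000 must stop, while one with the same count and organ signs put down to lupus, an infection or another drug has no stated mandatory stop. Eosinophilia was reported in the Phase 1 study in SLE (Protocol 2.3), and exclusion criterion [43] admits counts up to 3000 cells/µL, so the rule is not idle. At stake is continued dosing of an individual at a count the protocol itself treats as a reason to stop. Detection is not in doubt, since hematology is drawn at most visits.

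**Working it through.** The plan gives no figure to reproduce here; the check is one of logic. Set the two sub-rules against the possible symptom states.

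| Symptom state | Count >1500 to 5000 | Confirmed >5000, literal wording | Confirmed >5000, *asymptomatic* read as no eosinophil-related organ involvement | Confirmed >5000, after the fix |
|---|---|---|---|---|
| No symptoms | No stop | Stop (second sub-rule) | Stop | Stop |
| Organ involvement inconsistent with lupus or with history | Stop (first sub-rule) | Stop (first sub-rule) | Stop | Stop |
| Signs or symptoms attributed to lupus and fitting the history, or attributed to another cause | No stop | **Neither sub-rule met** | Stop | Stop |

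Only the third row is in question. Because the first sub-rule is triggered by inconsistency with lupus *and/or* history, a lupus attribution escapes it only if the findings fit both. The clause on other causes gives a second way out for new cardiac, pulmonary and skin findings. A participant who leaves by either route is not plainly asymptomatic. The column for counts up to 5000 is the same under every reading and is not changed by the fix.

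**Most exposure that could follow one such count** (Protocol 1.3, dosing and hematology rows):

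- Doses: 14 visits (V2 to V15), none at V3 or V15, so 14 − 2 = 12.
- Scheduled hematology after the first dose: V3 to V9 (7) + V11 + V13 + V15 = 10. All but V15 precede the last dose at V14, so 9.
- Assume the result returns after any dose given at the same visit. Later doses are then 11 if the count is first seen at V3 (V4 to V14), 5 if at V9 (V10 to V14), and 1 if at V13 (V14 only).

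These are ceilings, not expectations. The V3 case would need inaction through 8 further scheduled draws before the last dose (V4 to V9, V11, V13).

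**Distance from the entry limit.** (5000 − 3000)/3000 = 67%. This is arithmetic only and says nothing about how often such a rise occurs.

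**The case against.** The strongest answer is that the literal reading is not the natural one. Both sub-rules sit under one parent bullet. The first deals with hypereosinophilia with target organ involvement, and *asymptomatic* in the second is most naturally its complement. Criterion [7] supports this: if the word meant free of lupus symptoms, the rule would apply to almost nobody at entry. On that reading every row of the table is covered, and what remains is an undefined word. This largely stands as an account of intent, but the text does not state it, and a stopping rule should not rely on each site inferring it.

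The second answer is that other safeguards exist. Beyond the investigator-judgement bullet:

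- Protocol 8.2 tells the investigator to raise immediate safety concerns with the sponsor at once, to decide whether the participant continues on drug, and provides for blinded sponsor review at least quarterly.
- Protocol 8.2.5 calls for clinically significant abnormal results to be repeated.
- Protocol 7.1.2.2 allows temporary withholding.
- Protocol 10.1.5 lets the internal assessment committee review unblinded safety data periodically or ad hoc. The multi-participant trigger in 10.1.9 is therefore not the only way to reach that committee.

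These make a stop likely and divergent handling between sites less so. None makes the stop mandatory.

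Third, the way out of the first sub-rule is narrow: new cardiac, pulmonary and skin findings are presumed to be organ involvement, and evaluation against prior records is required. That limits the number affected without closing the gap.

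Fourth, the contrast with the cytopenia limits should not be pressed. They carry no symptom condition, but they sit under the same list of possible reasons and lack the explicit instruction to discontinue that both eosinophil sub-rules contain.

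Finally, redactions in 2.3, in a cross-reference in 7.1.1 and around 8.3.6 could hold eosinophil guidance. That cannot be settled either way.

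**Conclusion.** The point holds as a wording defect in a stated safety stop. At a confirmed count above 5000 cells/µL, the literal text leaves one symptom state without a mandatory stop, although the probable intent covers it. The conclusion rests on the readable text only.

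A reader might infer more: that the protocol lets symptomatic participants with very high counts continue unchecked, that most of the trial falls outside the rule because everyone enters with arthritis or rash, or that 11 of 12 doses would follow. The documents do not support these readings. Such counts would be seen, several routes allow or encourage a stop, the sensible meaning of *asymptomatic* includes participants with continuing baseline lupus activity, and the 11-dose figure requires everyone to ignore repeated results.

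No frequency for counts above 5000 is given, so the number affected is unknown; it is probably very small. The change is worth making because it is cheap, but it is not urgent.

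**What to change.** In the second hypereosinophilia sub-rule of Protocol 7.1.1, replace the opening words *Asymptomatic participants with* by *Participants not already discontinued under the preceding criterion, regardless of symptoms or their attribution, with*. Leave both thresholds (1500 and 5000 cells/µL) and the confirmatory repeat unchanged. The wording should not be limited to lupus symptoms, because the first sub-rule also releases findings with other causes, such as infection or another drug. Participants stopped under the first sub-rule still need no repeat test.

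Cost: one phrase, no new scheduled test, and one unscheduled repeat count per affected participant. If the broader meaning was intended all along, no intended decision changes. Otherwise there may be a few extra discontinuations, which Protocol 9.4.1 counts as nonresponse. With 70 per group (Protocol 9.2), each one in a would-be responder lowers that arm's Week 24 rate by 1/70, about 1.4 percentage points.
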